2.7.1 Adverse events (AEs)

Note that AEs which start during the core study and end prior to the core EOS are not recorded on the Medical History eCRF, nor the Adverse Event eCRF. These AEs are considered as the Medical History in the extension study, hence the data from the core AE will be programmatically merged with the Medical History eCRF. Therefore, these events are not included in any AE summaries or listings but will be included in Medical History listings.

Treatment-emergent Adverse Events: The primary summaries of AEs will be based on treatment-emergent adverse events (TEAE). A TEAE is defined as any AE that develops on/after the first injection of study treatment or any event already present that worsens following the first injection of study treatment.

The number (and percentage) of participants with TEAEs will be summarized separately for ocular (study eye and fellow eye) and non-ocular in the following ways:

- Overall summary of subjects with death, any TEAE, any severe TEAE, any study treatment related TEAE, any TEAE leading to study treatment discontinuation, any treatment-emergent serious AE (TESAE), any study treatment related TESAE;
- TEAE, TESAE by primary SOC and PT;
- TEAE by primary SOC, PT, and maximum severity
- TEAE by Standardized MedDRA Query (SMQ) and PT;
- TEAEs related to study treatment by primary SOC and PT;
- TEAEs leading to study treatment discontinuation by primary SOC.

A subject with multiple AEs within a primary SOC is only counted once towards the total of the SOC.

Ocular TEAE in the study eye with occurrence greater than or equal to 1% and non-ocular TEAE with occurrence greater than or equal to 2% will be summarized by PT.

Pre-treatment Adverse Events: In addition to TEAEs, AEs which start on/after day 1 of the extension study and prior to the date/time of the first injection of the study treatment in the extension study will be summarized using number and percentage of patients by ocular (study eye and fellow eye)/non-ocular, primary SOC and PT using the Enrollment Set.

Study-emergent Adverse Events: All AEs that occur during the on-treatment period (defined in Section 2.1.1) will be summarized separately for ocular (study eye and fellow eye) and non-ocular events using the Enrollment Set in the following ways:

- AEs by primary SOC and PT;
- SAEs by primary SOC and PT;
- SAEs by primary SOC and PT, and maximum severity;
- Study treatment related SAEs, by primary SOC and PT

All deaths, SAEs or AEs leading to permanent study treatment discontinuation during the study will be summarized.

Adverse events are coded using MedDRA terminology.

For the legal requirements of ClinicalTrials.gov and EudraCT, two tables are mandatory:

- <on-treatment/treatment emergent> adverse events which are not serious adverse events with an incidence greater than X%. Detailed threshold (X%) will be determined by safety disclosure
- <on-treatment/treatment emergent> serious adverse events and SAE suspected to be related to study treatment will be provided by system organ class and preferred term on the safety set population.

If for a same patient, several consecutive AEs (irrespective of study treatment causality, seriousness and severity) occurred with the same SOC and PT:

- a single occurrence will be counted if there is ≤ 1 day gap between the end date of the preceding AE and the start date of the consecutive AE
- more than one occurrence will be counted if there is > 1 day gap between the end date of the preceding AE and the start date of the consecutive AE

For occurrence, the presence of at least one SAE / SAE suspected to be related to study treatment / non-SAE has to be checked in a block e.g., among AE's in a ≤ 1 day gap block, if at least one SAE is occurring, then one occurrence is calculated for that SAE.

The number of deaths resulting from SAEs suspected to be related to study treatment and SAEs irrespective of study treatment relationship will be provided by SOC and PT.

2.7.1.1 Adverse events of special interest / grouping of AEs.

The number (%) of subjects with treatment-emergent AESIs will be summarized by category and PT.

A Case Retrieval Sheet (CRS) with the exact composition of the AE groupings is to be used to map reported AEs to the AESI groupings. This file may be updated (i.e., it is a living document) based on review of accumulating trial data, and therefore the groupings are also subject to potential change. The most up-to-date version of the CRS will be used at the time of the analysis.

AESIs related to the study treatment and/or study treatment procedure will be summarized by category and PT term.

2.7.2 Deaths

On-treatment deaths and all deaths including those that occurred outside the on-treatment period will be summarized by primary SOC and PT. A listing will also be provided.

2.7.3 Loss in best corrected visual acuity

Number and % of subjects who lost $\geq 15/ \geq 30$ letters in BCVA from baseline up to Week 56 will be presented for the study eye. Missing data will not be imputed. Number of subjects with $\geq 15/ \geq 30$ letter loss at the last visit will also be summarized. In addition, a listing for subjects who lost $\geq 15/ \geq 30$ letters in the study eye from the baseline at Week 56 will be provided.

2.7.4 Laboratory data

Not applicable.

2.7.5 Other safety data

2.7.5.1 Vital signs

Summary statistics of vital signs will be provided based on data from the on-treatment period except for baseline data which will be summarized where appropriate.

Clinically relevant abnormalities in vital signs data i.e., sitting blood pressure (systolic and diastolic pressure in mmHg) and pulse rate (beats per minute) will be listed by subject, and visit/study day and abnormalities as per normal range and critical values as per [Table 2-2](#) will be flagged.

Number (%) of participants with critical abnormalities will also be provided.

Table 2-2 Critical changes in vital signs

Variable	Category	Critical Values
----------	----------	-----------------

Systolic blood pressure (mmHg)	High	Either > 180 with an increase from baseline of the extension study > 30 or > 200 absolute
	Low	Either < 90 with a decrease from baseline of the extension study > 30 or < 75 absolute
Diastolic blood pressure (mmHg)	High	Either > 105 with an increase from baseline of the extension study > 20 or > 115 absolute
	Low	Either < 50 with a decrease from baseline of the extension study > 20 or < 40 absolute
Pulse rate (bpm)	High	Either > 120 with an increase from baseline of the extension study > 25 or > 130 absolute
	Low	Either < 50 with a decrease from baseline of the extension study > 30 or < 40 absolute

Summary statistics will also be provided by visits.

Intraocular pressure (IOP) measurements will be recorded in mmHg.

Summary statistics of pre-dose observed IOP values and change from baseline of the extension study for both study and fellow eyes will be presented by visit.

Furthermore, summary statistics of pre-dose and post-dose observed IOP values and respective change from pre-dose for the study eye will be presented by visit.

Listing of clinically significant elevations in pre- and post-dose IOP measurements for both study and fellow eyes will be provided by visit/study day and elevated IOPs (≥ 25 mmHg) will be flagged.

2.8 Pharmacokinetic endpoints

Not applicable.

2.9 PD and PK/PD analyses

[figure not shown]
Not applicable.

[figure not shown]
2.10 Patient-reported outcomes

Not applicable.

2.11 Biomarkers

Not applicable.

2.13 Interim analysis

Not applicable.

3 Sample size calculation

All participants who completed Week 64/EOS in the core study and meet all inclusion and exclusion criteria will be eligible for enrollment into the extension study. The initial sample size analyses assumed that all participants completing the core study and eligible for enrollment in the extension study will be enrolled in the extension study. After the protocol amendment, it is planned that approximately 250 participants will be enrolled the extension study. Simulation studies conducted before the urgent safety measures were introduced are described below.

Table 3-1 shows the distribution of duration as estimated based on simulation studies along with precision as estimated based on the simulations. Table 3-2 shows width of 95% CI as estimated based on a sample of size (number of participants completing the extension study) varying from 503 to 100. The numbers are chosen based on assuming that 90%/80%/70%/etc of participants from the core study enter the extension and also assuming that 10%/20%/30%/etc of participants drop out reaching EOS of the extension. Similarly, Table 3-3 shows 95% CI for the estimate in the change of BCVA, assuming that the observed change is -1 and the standard deviation of the change is 13.

For example, when the number of participants completing the extension study decreases from 503 to 212, width of the 95% CI increases from 5.8% to 9% for the estimated proportion of 12.7% participants being on the 16-weeks interval; and from 6.9% to 9.8% for the estimated proportion of 19.4% of participants being on 20-weeks interval. With the same reduction in the sample size, the 95% CI for the estimated change in BCVA goes from (-2.1, 0.14) to (-2.8, 0.8).

The 95% CI are obtained using PASS 11.

Table 3-1 Duration of intervals as estimated based on simulation studies

Interval duration	4-weeks	8-weeks	12-weeks	16-weeks	20-weeks
Frequency (SD as assessed by simulations)	8.6% (1.7%)	30.2% (1.9%)	29.2% (2.3%)	12.7% (1.7%)	19.4% (2.4%)

Table 3-2 Duration of intervals as estimated based on simulation studies and width of 95% confidence Interval

Duration of the treatment interval	4-weeks	8-weeks	12-weeks	16-weeks	20-weeks
Frequency (SD from simulations)	8.6% (1.7%)	30.2% (1.9%)	29.2% (2.3%)	12.7% (1.7%)	19.4% (2.4%)
N of participants completing the extension study	Width of 95% Confidence Interval				
503	4.9%	8.0%	7.9%	5.8%	6.9%
447	5.2%	8.5%	8.4%	6.2%	7.3%
391	5.6%	9.1%	9.0%	6.6%	7.8%
348	5.9%	9.6%	9.6%	7.0%	8.3%
304	6.3%	10.3%	10.2%	7.5%	8.9%
250	7%	11.4%	11.3%	8.3%	9.8%
212	7.5%	12.4%	12.2%	9%	10.6%
200	8.3%	13.1%	13.0%	9.7%	11.4%
170	9.0%	14.3%	14.2%	10.6%	12.4%
150	9.6%	15.2%	15.1%	11.3%	13.2%
120	10.9%	17.1%	16.9%	12.7%	14.9%
100	12.0%	18.8%	18.6%	14.0%	16.3%

Table 3-3 95% Confidence interval for BCVA change assuming SD of the change is 13

N of participants completing the extension study	95% Confidence Interval of BCVA change assuming the observed change is -1.
503	(-2.1, 0.14)
447	(-2.2, 0.21)
391	(-2.3, 0.29)
348	(-2.4, 0.37)
304	(-2.5, 0.47)
250	(-2.6, 0.62)
212	(-2.8, 0.76)
200	(-2.8, 0.81)
170	(-3.0, 0.97)
150	(-3.1, 1.1)
120	(-3.4, 1.4)
100	(-3.6, 1.6)

4 Change to protocol specified analyses

Added in the SAP is the secondary endpoint characterizing the change from the baseline of the core study for all participants and per randomized arm in the core study. Specifically,

- Change in CSFT from the baseline of the core study by visit.
- Average change in CSFT from the baseline of the core study at Week 52 and Week 56.
- Change in BCVA from the baseline of the core study by visit.
- Average change in BCVA from the baseline of the core study at Week 52 and Week 56.

Statistical analyses are described in [Section 2.6.1](#).

BCVA categories are the same as in the SAP for the core study.

5 Appendix

5.1 Imputation rules

Not applicable.

5.1.1 Study drug

Not applicable.

5.1.2 AE date imputation

Adverse event end date imputation

1. If the AE end date month is missing, the imputed end date should be set to the earliest of the (31DECYYYY, date of death).
2. If the AE end date day is missing, the imputed end date should be set to the earliest of the (last day of the month, date of death).
3. If AE year is missing or AE is ongoing, the end date will not be imputed.

If the imputed AE end date is less than the existing AE start date then use AE start date as AE end date.

Adverse event start date imputation

The following table explains the notation used in the logic matrix. Please note that completely missing start dates will not be imputed.

The following table explains the notation used in the logic matrix.

	Day	Month	Year
Partial Adverse Event Start Date	Not used	MON	YYYY
Treatment Start Date	Not used	TRTM	TRTY

The following matrix explains the logic behind the imputation.

	MON MISSING	MON < TRTM	MON = TRTM	MON > TRTM
YYYY MISSING	(1) No convention	(1) No convention	(1) No convention	(1) No convention
YYYY < TRTY	(2.a) Before Treatment Start	(2.b) Before Treatment Start	(2.b) Before Treatment Start	(2.b) Before Treatment Start
YYYY = TRTY	(4.a) Uncertain	(4.b) Before Treatment Start	(4.c) Uncertain	(4.c) After Treatment Start
YYYY > TRTY	(3.a) After Treatment Start	(3.b) After Treatment Start	(3.b) After Treatment Start	(3.b) After Treatment Start

Before imputing AE start date, find the AE start reference date.

1. If the (imputed) AE end date is complete and the (imputed) AE end date < treatment start date then AE start reference date = min (informed consent date, earliest visit date).
2. Else AE start reference date = treatment start date

Impute AE start date -

1. If the AE start date year value is missing, the date uncertainty is too high to impute a rational date. Therefore, if the AE year value is missing, the imputed AE start date is set to NULL.
2. If the AE start date year value is less than the treatment start date year value, the AE started before treatment. Therefore:
 - a. If AE month is missing, the imputed AE start date is set to the mid-year point (01JulYYYY).
 - b. Else if AE month is not missing, the imputed AE start date is set to the mid-month point (15MONYYYY).
3. If the AE start date year value is greater than the treatment start date year value, the AE started after treatment. Therefore:
 - a. If the AE month is missing, the imputed AE start date is set to the year start point (01JanYYYY).
 - b. Else if the AE month is not missing, the imputed AE start date is set to the later of (month start point (01MONYYYY), AE start reference date + 1 day).
4. If the AE start date year value is equal to the treatment start date year value:
 - a. And the AE month is missing the imputed AE start date is set to the AE reference start date + 1 day.
 - b. Else if the AE month is less than the treatment start month, the imputed AE start date is set to the mid-month point (15MONYYYY).

- c. Else if the AE month is equal to the treatment start date month or greater than the treatment start date month, the imputed AE start date is set to the later of (month start point (01MONYYYY), AE start reference date + 1 day).

If complete (imputed) AE end date is available and the imputed AE start date is greater than the (imputed) AE end date, then imputed AE start date should be set to the (imputed) AE end date.

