5.1.3 Concomitant medication date imputation

1. If the CM end date year value is missing, the date uncertainty is too high to impute a rational date. Therefore, if the CM end year value is missing or ongoing, the imputed CM end date is set to NULL.
2. Else, if the CM end date month is missing, the imputed end date should be set to the earliest of the (treatment follow up period date, 31DECYYYY, and date of death).
3. If the CM end date day is missing, the imputed end date should be set to the earliest of the (treatment follow up period date, last day of the month, date of death).

If the imputed CM end date is less than the existing CM start date, use the CM start date as the imputed CM end date.

Concomitant medication start date imputation

To classify a medication as prior and prior/concomitant, it may be necessary to impute the start date.

Completely missing start dates will be set to one day prior to treatment start date. As a conservative approach, such treatments will be classified as prior and concomitant (and summarized for each output).

Concomitant treatments with partial start dates will have the date or dates imputed. The following table explains the notation used in the logic matrix

	Day	Month	Year
Partial CMD Start Date	Not used	MON	YYYY
Treatment Start Date	Not used	TRTM	TRTY

The following matrix explains the logic behind the imputation.

	MON MISSING	MON < TRTM	MON = TRTM	MON > TRTM
YYYY MISSING	(1) Uncertain	(1) Uncertain	(1) Uncertain	(1) Uncertain
YYYY < TRTY	(2. a) Before Treatment Start	(2. b) Before Treatment Start	(2. b) Before Treatment Start	(2. b) Before Treatment Start

YYYY = TRTY	(4. a) Uncertain	(4. b) Before Treatment Start	(4.a) Uncertain	(4. c) After Treatment Start
YYYY > TRTY	(3. a) After Treatment Start	(3.b) After Treatment Start	(3.b) After Treatment Start	(3.b) After Treatment Start

1. If the CM start date year value is missing, the imputed CM start date is set to one day prior to treatment start date.
2. If the CM start date year value is less than the treatment start date year value, the CM started before treatment. Therefore:
 - a. If the CM month is missing, the imputed CM start date is set to the mid-year point (01JulYYYY).
 - b. Else if the CM month is not missing, the imputed CM start date is set to the mid- month point (15MONYYYY).
3. If the CM start date year value is greater than the treatment start date year value, the CM started after treatment. Therefore:

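### The AE start-date rules in SAP 5.1.2 give no class to an AE without a start year and set no floor at extension Day 1, so some AEs may be left out of the tables that select on onset

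*SAP*

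**What the plan says.** **Missing year.** SAP 5.1.2 states: "Please note that completely missing start dates will not be imputed". Rule 1 adds: "Therefore, if the AE year value is missing, the imputed AE start date is set to NULL". The logic matrix labels these cells as having no convention. No class is assigned afterwards.

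**Known year, start before the treatment month or year.** Rule 4.b reads: "the AE month is less than the treatment start month, the imputed AE start date is set to the mid-month point". Rule 2.b does the same when the start year is earlier than the treatment year. Rule 2.a sets 1 July of the start year when the month is also missing. None of the three mentions Day 1.

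**Reference date.** For an AE that ended before the first injection, the reference date is the earlier of the consent date and the first visit. Rule 4.a then sets the start to that date plus one day. Protocol Section 3 lets consent be signed before the core Week 64 visit, which is extension Day 1 (SAP 2.1.1).

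**Tables.** SAP 2.7.1: "A TEAE is defined as any AE that develops on/after the first injection of study treatment", with a second limb for events already present that worsen afterwards. Pre-treatment AEs are "AEs which start on/after day 1 of the extension study and prior to the date/time of the first injection". Study-emergent AEs are those that occur in the on-treatment period, which the SAP starts at Day 1. The AESI table (SAP 2.7.1.1) is limited to treatment-emergent events.

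**Medications.** For completely missing start dates, SAP 5.1.3 imputes the day before treatment start and says: "As a conservative approach, such treatments will be classified as prior and concomitant".

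**The concern.** AE occurrence is the study's safety endpoint, yet an AE without a start year has less guidance than a medication without one. An undated event cannot be shown to have begun on or after the first injection, so whether it is counted is left to programming. With about 250 participants, a single event can decide whether a preferred term is displayed. SAP 2.7.1 tabulates ocular study-eye TEAEs at 1% or more: 3/250 = 1.2% is shown, 2/250 = 0.8% is not.

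The rules are also anchored on the first extension injection, as if that were study entry. Here it usually is not. In the SAP 2.1.1 example, a 16-week interval starting at core Week 56 ends at Week 72, which is 72 − 64 = 8 weeks after Day 1. The protocol 6.7.2 example (Week 60 + 12) gives the same 8 weeks. AEs arising in this gap belong in the pre-treatment table, and the rules can date them out of it.

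**Working it through.** The documents give no figure to reproduce. The check applies the 5.1.2 rules to specific dates, then to a calendar of dates.

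**1. Missing year.** The start is null in every case, whatever the end date or injection date.

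**2. Examples of dating before Day 1.**
- Day 1 20 Sep 2021, injection 15 Nov 2021, AE recorded as Sep 2021: rule 4.b gives 15 Sep 2021.
- Day 1 20 Nov 2021, injection 15 Jan 2022, AE recorded as Nov 2021: rule 2.b gives 15 Nov 2021. Recorded only as 2021: rule 2.a gives 1 Jul 2021.
- Consent 1 Jun 2021, Day 1 15 Jun 2021, injection 10 Aug 2021, AE recorded as 2021 and ended 20 Jul 2021: rule 4.a gives 2 Jun 2021.

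**3. How often.** Assumptions: Day 1 equally likely on each day of 2021, gap of G days (4, 8, 12 or 14 weeks), onset equally likely on each gap day, consent on Day 1.

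*Day missing.* The 15th precedes Day 1 only if Day 1 is the 16th or later and onset is in the same month. The number of (Day 1, onset) pairs is 16·17/2 = 136 in a 31-day month, 15·16/2 = 120 in a 30-day month and 13·14/2 = 91 in February. Over the year: 7·136 + 4·120 + 91 = 1,523. The share is 1,523/(365·G).

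*Day and month missing.* Every onset in a year before the injection year goes to 1 July, ahead of Day 1. The pairs number G(G+1)/2, so the share is (G+1)/730.

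| Gap | Day missing: before Day 1 | Day and month missing: before Day 1 | Ongoing at injection, dated after it: day missing | Same: day and month missing |
|---|---|---|---|---|
| 4 weeks | 14.9% | 4.0% | 52.3% | 96.0% |
| 8 weeks | 7.5% | 7.8% | 26.3% | 92.2% |
| 12 weeks | 5.0% | 11.6% | 17.5% | 88.4% |
| 14 weeks | 4.3% | 13.6% | 15.0% | 86.4% |

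Running the coded rules over all dates gives the same first two columns as the formulas. The last two columns come from that run and concern gap AEs still ongoing at injection, which rules 4.a and 4.c move to the day after it or later.

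**4. Earlier consent.** With consent 14 or 28 days before Day 1, all gap AEs with day and month missing that ended before injection are dated before Day 1. With only the day missing, the share changes only at the 4-week gap, from 14.9% to 19.8% of those that ended before injection.

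**5. True post-injection AEs with a known year.** None of 4,270,500 scenarios was dated before the first injection. This follows from the rules: from the treatment month onward they give a date after treatment start, and the cap at the end date cannot go below the true onset.

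**6. Participants never injected.** Every known-year rule compares the AE year, and where needed the month, with those of treatment start. These participants have no treatment start. Protocol 8.1.1 foresees them, and SAP 2.7.1 uses the Enrollment Set for the pre-treatment and study-emergent tables. No rule can impute their partial dates.

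**The case against.** A reader might infer that these AEs meet no table definition and vanish from the safety summaries. The documents do not support that. A null date is not an exclusion rule, and the SAP nowhere says undated AEs are left out; the programming specifications, which are not among the documents, may settle it. The TEAE definition has its worsening limb. Study-emergent AEs need only *occur* in the period, so an ongoing AE with an early imputed start can still qualify. SAP 2.7.1 also summarizes all deaths, SAEs and AEs leading to permanent discontinuation during the study. Loss from every AE table is clearest for a non-serious pre-injection AE that neither worsens nor leads to discontinuation and is dated before Day 1, and then only if *occur* is read as *start*, as in protocol 12.5.2.

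A reader might also infer that the error always lowers AE counts. It does not: rules 4.a and 4.c move many ongoing gap AEs into the TEAE tables. Nor does the Day 1 misdating thin the AESI table. A gap AESI that does not worsen after injection is outside that table even when perfectly dated.

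Three further points have weight. Protocol 10.1.1 asks for start and end dates as far as possible and 11.2 has missing values queried, so a missing year should be rare. Protocol 12.5.2 has pre-injection AEs listed only, although protocol 12.1 and the SAP summarize them. The medication rule is a different convention, not a contradiction, and 5.1.2 gives its reason for not imputing a year.

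What stands is that declining to impute a date does not remove the need to state a class, and that the stated rules can put a post-Day-1 AE before Day 1.

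**Conclusion.** The point holds in limited form. The main gap is the missing class for AEs without a start year, because it reaches the TEAE and AESI tables. The missing Day 1 floor is smaller: about 4% to 15% of gap AEs with partial dates, resting on the assumed calendar, uniform onset, 4- to 14-week gaps and consent on Day 1; earlier consent raises it. It affects the pre-treatment table and possibly the study-emergent table, not true TEAEs. The gap for participants never injected is real but confined to partial dates in people outside the FAS. The absolute number of events cannot be stated, because the documents do not give the frequency of partial or missing dates.

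**What to change.** Add three rules to SAP 5.1.2 before database lock:

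- **(a)** Count an AE with a missing start year as treatment-emergent, unless a complete end date precedes the first injection or the participant was never injected. In those cases count it as pre-treatment, unless a complete end date precedes Day 1.
- **(b)** Where the recorded partial date allows onset on or after Day 1, set the imputed start to the later of the rule's date and Day 1. The condition is needed because protocol 10.1.1 defines AEs from consent, which may precede Day 1; an unconditional floor would move AEs known to be earlier into the extension.
- **(c)** For participants never injected, use Day 1 as the reference date in place of treatment start.

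By construction, (a) gives every AE without a start year a stated treatment, and (b) brings the share of the AEs it covers that are dated before Day 1 to zero. The cost is a few appendix lines and minor programming, with no new data. The downside is that a few AEs that really started earlier may be counted in the extension or as treatment-emergent.
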